7.5. Medical History and Medical Conditions Present at Entry

Complete medical history will be obtained at screening. Medical history records will be coded, using the current version of Medical Dictionary for Regulatory Activities (MedDRA), and summarized descriptively using the safety population.

7.6. Prior Medication History and Medications Present at Entry

Medications will be coded using the most recent version of the World Health Organization Drug Dictionary (WHODRUG). Prior medications will be summarized descriptively by treatment group for the safety population. Previous treatments that have been stopped prior to date of first study drug dose will be summarized separately from medications that were started and continued into the study drug treatment period.

A summary of prior medications with indication of COVID-19 will also be provided.

8. EFFICACY

8.1. General Considerations

Where adjustment for stratification factors (age and region) is specified, the group will be based on the randomization assignment. All efficacy endpoints will be evaluated post treatment.

8.2. Testing Statistical Assumptions Including Comparability at Baseline

No testing will be carried out on baseline characteristics.

The primary analysis method for comparison of treatment groups is the Cochran-Mantel-Haenszel (CMH) test. For CMH, small cell counts could be problematic. The Mantel-Fleiss criterion will be used to assess the validity of the chi-square approximation for the distribution of the Mantel-Haenszel statistic in the analyses. In the event there is indication that the test statistic may not be valid, strata will be removed from the analysis until the criterion for validity is met. Any removal of strata will be carried out in the following order: age first, then region. If all strata are indicated to be removed, then an unstratified comparison will be carried out.

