6.1. General Summary Table and Individual Subject Data Listing Considerations

Unless otherwise specified, continuous variables will be summarized by using the number of non-missing observations, arithmetic mean, standard deviation (SD), minimum, first quartile, median, third quartile and maximum values as summary statistics; categorical variables will be summarized by using the frequency count and the percentage of subjects in each category as summary statistics. Descriptive summaries will be tabulated by treatment group.

When a summary tabulates the number of subjects, subjects will only be counted once for a category (e.g., a particular adverse event type, a particular adverse event term, a particular concomitant medication) unless otherwise specified.

All statistical tests will be performed at a 0.025 significance level using one-sided tests, unless otherwise noted. Statistical tests will use stratification factors (age and region) according to randomization. Stratification factors may need to be removed or have their levels combined so that low or zero counts in one stratum do not invalidate relevant statistical tests.

Unless otherwise specified, all efficacy and virology analyses will be performed on the modified intent-to-treat (mITT) analysis populations for each stratum. All safety analyses, demographics, and baseline characteristics will be performed on the safety population. Refer to Section 6.5 for details on analysis population definitions.

All Safety, Efficacy, and Tolerability data will be listed. In cases where additional information may be helpful, considerations for listings will be noted in this document.

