8.5. Multiple Comparisons and Multiplicity

If a statistically significant result is found on the test of the primary endpoint, sequential testing will be performed for the secondary endpoints in the following order. When endpoint is tested for both Day 29 and Day 60, the order will be Day 29 first, followed by D60.

- 1. Proportion of subjects in the supportive-care-only population with all-cause hospitalization or all-cause death through Day 60
- 2. Proportion of subjects in the supportive-care-only population with all-cause hospitalization, all-cause death, or COVID-19 related medically attended visits through Day 29 and Day 60.
- 3. Proportion of subjects in the supportive-care-only population with COVID-19-related hospitalization or who died due to any cause death through Day 29 and Day 60
- 4. Proportion of subjects in the supportive-care-only population who died due to any cause through Day 29 and Day 60
- 5. Proportion of subjects in the supportive-care-only population with COVID-19-related complications (e.g., death, hospitalization, radiologically confirmed pneumonia, acute respiratory failure, sepsis, coagulopathy, pericarditis/myocarditis, cardiac failure) through Day 29 and Day 60
- 6. Proportion of subjects in the supportive-care-only population with COVID-19-related medically attended visits (hospitalization, ER visit, urgent care or physician's office visit or telemedicine visit) or who died due to any cause through Day 29 and Day 60.
- 7. Proportion of subjects in the supportive-care-only population with COVID-19-related medically attended visits through Day 29 and Day 60
- 8. Proportion of subjects in the supportive-care-only population with COVID-19 symptom relapse through Day 29
- 9. Proportion of subjects in the supportive-care-only population with viral load rebound through Day 29
- 10. Proportion of subjects in the combination-antiviral population with COVID-19 symptom relapse through Day 29
- 11. Proportion of subjects in the combination-antiviral population with viral load rebound through Day 29

Version 5 June 24, 2024

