8.6.1. Primary Efficacy Analysis

The primary efficacy objective of this study is to evaluate the efficacy of BEM based on the proportion of subjects who are hospitalized for any cause or who died due to any cause through Day 29 in the supportive-care-only population. Hospitalization is defined as >24 hours of acute care, in a hospital or similar acute care facility, including Emergency Rooms or temporary facilities instituted to address medical needs of those with severe COVID-19 during the COVID-19 pandemic. This includes specialized acute medical care unit within an assisted living facility

or nursing home. This does not include hospitalization for the purposes of public health and/or clinical trial execution. Furthermore, scheduled hospitalization for a pre-planned procedure (including chemotherapy) to treat a pre-existing condition that has not worsened is not an SAE, and would not be considered a hospitalization for the purposes of the efficacy analyses. A pre-existing condition is a clinical condition that is diagnosed prior to the use of study drug and is documented in the subject's medical history.

The primary estimand is the difference in the proportions of subjects who are hospitalized for any cause or who died due to any cause through Day 29 in the supportive-care-only population, and the primary treatment effect comparison will be between the BEM arm and the placebo arm. This proportion will be compared between the BEM and placebo arms using a CMH test adjusted for the stratification factors of age and region. The CMH p-value and estimated common risk difference, odds ratio and relative risk, along with the corresponding 95% confidence intervals (CIs) for these estimates, will be presented. The confidence interval for the common risk difference will be computed using the Klingenberg method⁵. Summary tables will include tabulation of the number of events, by type of event (hospitalization, death).

The analysis will be carried out using the following sample SAS code:

Each region-age combined strata has a 2×2 table with counts for BEM hospitalized, BEM not hospitalized, Placebo hospitalized, and Placebo not hospitalized. In total there will be 8 strata. When low number of events happens and the model can't be carried out, removal of strata will be carried out in the following order: age first, then region. If all strata are indicated to be removed, then an unstratified comparison will be carried out.

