8.6.2. Sensitivity Analyses of the Primary Efficacy Results

Planned supplemental analyses to support the primary endpoint result are identified in Table 4. The supplemental analyses investigate the impact of significant COVID-19 rescue therapy and data handling for early study discontinuations. For the CMH and stratified log-rank analyses, incorporation of strata will be the same as that used for the primary analysis. The Kaplan-Meier and log-rank analyses will include all data to Day 29.

The primary endpoint may also be analyzed for each of the subgroups defined in Section 8.4 .

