8.7. Analysis of the Secondary Efficacy Endpoints

The following secondary endpoints will be analyzed using the same approach as that for the primary endpoint:

- Proportion of subjects in the supportive-care-only population with all-cause hospitalization or all-cause death through Day 60
- Proportion of subjects in the supportive-care-only population with all-cause hospitalization, all-cause death, or COVID-19 related medically attended visits through Day 29 and Day 60.
- Proportion of subjects in the supportive-care-only population with COVID-19-related hospitalization or who died due to any cause death through Day 29 and Day 60
- Proportion of subjects in the supportive-care-only population who died due to any cause through Day 29 and Day 60
- Proportion of subjects in the supportive-care-only population with COVID-19-related complications (e.g., death, hospitalization, radiologically confirmed pneumonia, acute respiratory failure, sepsis, coagulopathy, pericarditis/myocarditis, cardiac failure) through Day 29 and Day 60
- Proportion of subjects in the supportive-care-only population with COVID-19-related medically attended visits (hospitalization, ER visit, urgent care or physician's office visit or telemedicine visit) or who died due to any cause through Day 29 and Day 60.
- Proportion of subjects in the supportive-care-only population with COVID-19-related medically attended visits through Day 29 and Day 60
- Proportion of subjects in the supportive-care-only population with COVID-19 symptom relapse through Day 29
- Proportion of subjects in the supportive-care-only population with viral load rebound through Day 29
- Proportion of subjects in the combination-antiviral population with COVID-19 symptom relapse through Day 29
- Proportion of subjects in the combination-antiviral population with viral load rebound through Day 29

COVID-19 related complications will be adjudicated by blinded medical review prior to analysis.

The proportion of subjects with COVID-19 symptom relapse in each population through Day 29 will be tabulated. This summary will be based on the response to "Have your COVID-19 symptoms returned after previously improving?" (i.e., question 4 in the Symptom Diary, see Section 11.1).

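### Does the low-event fallback for the CMH test leave the all-cause death comparison undefined?

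*SAP*

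**What the plan says.** SAP 8.2 makes CMH the main method for comparing the arms and uses the Mantel-Fleiss criterion to judge whether its chi-square approximation can be trusted. On failure, "strata will be removed from the analysis until the criterion for validity is met", age before region. The rule then closes: "If all strata are indicated to be removed, then an unstratified comparison will be carried out". The text gives no numerical cut-off and does not name the final test.

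Two other sections describe the same step with different triggers. SAP 6.1 allows factors to be dropped or levels merged "so that low or zero counts in one stratum do not invalidate relevant statistical tests". SAP 8.6.1 repeats the removal order but starts it "When low number of events happens and the model can't be carried out". It also announces sample SAS code, which is absent from the text as extracted, and fixes the interval: "The confidence interval for the common risk difference will be computed using the Klingenberg method".

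SAP 8.6.2 says of the supplemental analyses of the primary endpoint that "incorporation of strata will be the same as that used for the primary analysis". SAP 8.7 carries the method to the secondary endpoints: "The following secondary endpoints will be analyzed using the same approach as that for the primary endpoint". In SAP 8.5, step 4 of the fixed sequence is "Proportion of subjects in the supportive-care-only population who died due to any cause through Day 29 and Day 60", with Day 29 tested before Day 60.

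**The concern.** Three things look wrong on a first reading.

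- The remedy seems unable to do its job. If the criterion fails because events are few, pooling strata does not raise the total number of events.
- The rule ends in a comparison without a named test. With a handful of deaths, a chi-square and an exact test can fall on opposite sides of 0.025.
- Three sections state three triggers, and SAP 8.7 does not say outright that the check is repeated for each secondary endpoint.

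The stake is step 4. If all-cause death fails at Day 29, its Day 60 test and steps 5 to 11 are not tested. Choosing between two tests after seeing the death counts would be a data-dependent decision at a confirmatory gate.

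**Working it through.** **Inputs.** One-sided 0.025 (SAP 4.3). 1:1 allocation (SAP 4.4). Rates of 4% v 1.6%, with 3% placebo as the alternative (SAP 4.3.1). 2100 evaluable, so 1050 per arm (SAP 11.2). Eight age-by-region strata (SAP 8.6.1). Two inputs are assumptions because the documents do not give them: the Mantel-Fleiss cut-off c (5 as base case, range 3 to 10) and the placebo death rate (0.2% to 0.6%).

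**Plan's own figure.** The two-proportion formula for 4% v 1.6% with 90% power returns 991 per arm, as in SAP 11.2. 2 × 991 × 1.055 = 2091, which the SAP takes as 2100; 2100/0.95 = 2210.5, against 2210 in the SAP.

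**Step 1: what the criterion can reach.** The Mantel-Fleiss value is MF = min(Σm − ΣL, ΣU − Σm). Here m is the expected event count in one arm of a stratum, and L and U are the smallest and largest counts possible given the margins. The two terms add to ΣU − ΣL, which is at most the total number of events E. Hence MF ≤ E/2 under any stratification, and MF > c is impossible when E ≤ 2c. For c = 5 that means 10 or fewer events. In simulated trials, mean MF at E = 10 was 4.993 with eight strata, 4.994 with region only and 4.995 with none.

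**Step 2: the primary endpoint.** Expected events are 1050 × (0.04 + 0.016) = 58.8, so MF is about 29. At the lower rate they are 1050 × (0.03 + 0.012) = 44.1, so MF is about 22. The fallback is not reached.

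**Step 3: which splits depend on the test.** For 0 v 4 deaths, the pooled rate is 4/2100 = 0.001905 and the difference is 4/1050 = 0.003810. Then z = 0.003810/√(0.001905 × 0.998095 × 2/1050) = 2.00 and one-sided p = 0.0226. One-stratum CMH gives 0.0227. The exact p is the hypergeometric probability that all four deaths fall on placebo, 0.0623. With 10 or fewer deaths, only three splits disagree at 0.025:

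| BEM v placebo | Chi-square p | Exact p | 95% Klingenberg interval |
|---|---|---|---|
| 0 v 4 | 0.0226 | 0.0623 | −0.75% to −0.01% |
| 0 v 5 | 0.0126 | 0.0311 | −0.89% to −0.06% |
| 1 v 7 | 0.0168 | 0.0349 | −1.10% to −0.04% |

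The interval specified in SAP 8.6.1 excludes zero in all three, in agreement with the chi-square.

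**Step 4: is the chi-square safe here?** With binomial deaths in each arm and no treatment effect, its type I error is 2.1%, 2.3% and 2.2% at death rates of 0.2%, 0.3% and 0.4%. The corresponding figures are 0.3%, 0.8% and 1.2% if an exact test is used at 10 or fewer deaths.

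**Step 5: do the triggers matter?** In simulated sets of 2100 subjects with 1 to 10 deaths (assumed region shares 25/35/15/25%, half aged 65 or older, doubled risk in that half), the SAP 8.2 trigger removed all strata in 100% and the SAP 8.6.1 trigger was met in 0%. Even so, eight-stratum CMH and unstratified chi-square gave the same verdict in at least 99.8%.

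**Step 6: what an exact test would change.** Chance of passing step 4 at Day 29, chi-square v exact used only at 10 or fewer deaths:

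| Placebo death rate | 60% reduction | 80% reduction |
|---|---|---|
| 0.2% | 7.2% v 0.9% | 10.8% v 1.4% |
| 0.4% | 16.2% v 7.4% | 31.3% v 13.4% |
| 0.6% | 22.3% v 17.2% | 45.4% v 32.5% |

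At 0.4% and a 60% reduction the gap is 6.7, 8.8 and 9.3 points for c = 3, 5 and 10.

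**The case for a change.** The strongest case for a change is that SAP 8.2 states a validity check and then ends in a test that still fails it. A careful statistician who had just seen the criterion rejected might turn to an exact test, and nothing in the text forbids that. Ten or fewer deaths is plausible: it is 17% to 23% of the expected primary events (10/58.8 and 10/44.1). The earlier outpatient Phase 3 study (Protocol 1.2.1) had 11 COVID-19 hospitalizations and no deaths, though that is weak evidence. A few sentences written before unblinding would close the question.

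Much of this stands. The bound E/2 is algebra and does not depend on the cut-off; removing strata does not repair the approximation at low counts; and the three sections do word the trigger differently.

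What does not stand is the step from an unnamed test to an open choice. The sections prescribe CMH, carry it to the secondary endpoints, and remove strata from it; what is left is CMH with one stratum. The exact test would have to be brought in from outside the available text, and it would disagree with the specified interval in exactly the splits at issue. SAP 8.2 also does not promise that removal always succeeds, since its last sentence provides for the case where it does not. On repeating the check, SAP 8.2 speaks of analyses in the plural and SAP 8.7 carries the approach to each endpoint. SAP 8.6.2 concerns only supplemental analyses of the primary endpoint, so it does not conflict.

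**Conclusion.** No change to the plan is needed. Read as written, the fallback leads to a one-stratum CMH, practically the Pearson chi-square. Its type I error at the assumed death rates of 0.2% to 0.4% stays below 2.5%. Because it agrees with the stratified test in at least 99.8% of simulated low-count sets, the differing triggers have no practical consequence. The missing cut-off has little weight either, since with or without strata the verdict is nearly always the same. The SAS code announced in SAP 8.6.1 may name the cut-off or the test, and its absence from the extracted text cannot be held against the plan.

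The reach is also narrow. The primary endpoint is untouched. Step 4 is tested only after the primary and five further tests have succeeded (step 1, then steps 2 and 3 at Day 29 and Day 60). The pass probabilities above are not conditional on that success. Naming the chi-square would only record what the text already implies. An exact test would lower the chance of passing step 4 by about 5 to 9 points at a 60% reduction and placebo death rates of 0.2% to 0.6%, and could not reject with five or fewer deaths, while correcting no inflation of error.

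The conclusion rests on assumed death rates, assumed stratum shares in the simulation, and the reading that stripping strata from a CMH test leaves a CMH test. If the sponsor in fact intended an exact test, step 4 would be affected to the extent shown; the available text gives no sign of that.

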8.3. Statement of the Null and Alternate Hypotheses

The null hypothesis is that the likelihood of all-cause hospitalization or death to Day 29 is the same between treatment groups in the supportive care population. The likelihood of the event is estimated by the proportion of subjects with the event, i.e., the primary endpoint.

The alternative hypothesis is that the treatment groups differ in the likelihood of all-cause hospitalization or death to Day 29, with the rate being lower in the BEM arm as the one-sided (0.025 level) alternative of interest.

8.4. Subgroup Analyses

To examine the robustness of the treatment effect, estimates of the difference between treatments in the proportions of subjects in the supportive-care-only population who are hospitalized for any cause or who died due to any cause through Day 29 (i.e., the primary endpoint) will be computed with corresponding 95% confidence intervals, per Wilson (Score) method without continuity correction, for the subgroups listed below. Estimates with confidence intervals will be presented in forest plots.

- Geographic region (North America, Europe, Asia, ROW)
- Age (<65, ≥ 65 years)
- Sex (female, male)
- Race
- Time from onset of symptoms (≤ 3 days, > 3 days)
- Baseline serology status (positive, negative)
- Baseline viral lineage (as applicable)
- COVID-19 vaccination status

Version 5 June 24, 2024

- Age ($< 80, \ge 80$)
- BMI ($<30, \ge 30$)
- Diabetes mellitus (yes, no)
- Cardiovascular disease or hypertension (yes, no)
- Chronic lung disease (yes, no)
- Immunocompromised/immunosuppressed (yes, no)
- Baseline viral load (<median, >=median).

8.5. Multiple Comparisons and Multiplicity

If a statistically significant result is found on the test of the primary endpoint, sequential testing will be performed for the secondary endpoints in the following order. When endpoint is tested for both Day 29 and Day 60, the order will be Day 29 first, followed by D60.

- 1. Proportion of subjects in the supportive-care-only population with all-cause hospitalization or all-cause death through Day 60
- 2. Proportion of subjects in the supportive-care-only population with all-cause hospitalization, all-cause death, or COVID-19 related medically attended visits through Day 29 and Day 60.
- 3. Proportion of subjects in the supportive-care-only population with COVID-19-related hospitalization or who died due to any cause death through Day 29 and Day 60
- 4. Proportion of subjects in the supportive-care-only population who died due to any cause through Day 29 and Day 60
- 5. Proportion of subjects in the supportive-care-only population with COVID-19-related complications (e.g., death, hospitalization, radiologically confirmed pneumonia, acute respiratory failure, sepsis, coagulopathy, pericarditis/myocarditis, cardiac failure) through Day 29 and Day 60
- 6. Proportion of subjects in the supportive-care-only population with COVID-19-related medically attended visits (hospitalization, ER visit, urgent care or physician's office visit or telemedicine visit) or who died due to any cause through Day 29 and Day 60.
- 7. Proportion of subjects in the supportive-care-only population with COVID-19-related medically attended visits through Day 29 and Day 60
- 8. Proportion of subjects in the supportive-care-only population with COVID-19 symptom relapse through Day 29
- 9. Proportion of subjects in the supportive-care-only population with viral load rebound through Day 29
- 10. Proportion of subjects in the combination-antiviral population with COVID-19 symptom relapse through Day 29
- 11. Proportion of subjects in the combination-antiviral population with viral load rebound through Day 29

Version 5 June 24, 2024

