8.3. Statistical Methods

The primary and secondary efficacy analyses will be conducted using the mITT-S population. Efficacy analyses will be repeated using the mITT-C population.

Safety analyses will be performed on the safety population, which consists of all subjects who received at least one dose of study drug. In all safety analyses, subjects will be grouped according to the treatment that the subjects actually received rather than the treatment assigned at randomization. Here, treatment will be considered as BEM monotherapy and placebo for subjects in the supportive-care-only population and as BEM combination and compatible antiviral in the combination antiviral population.

Demographics and baseline characteristics will be summarized by treatment group and overall for each analysis population. Disposition, with respect to both treatment and study completion, will be summarized by treatment group and overall with reasons for discontinuation tabulated.

For continuous variables, descriptive statistics will include the following information: the number of patients reflected in the calculation (n), mean, standard deviation, Q1, median, Q3, minimum, and maximum. For categorical or ordinal data, frequencies and percentages will be displayed for each category.

Time-to-event endpoints will be analyzed using Kaplan-Meier methods for estimation and log-rank test for treatment comparison.

Data handling for quantitative data that are reported as less than the lower limit of quantification, as well as values reported greater than the upper limit of quantification, will be described in the SAP.

In general, data will be considered as observed, ie, values for missing data will not be imputed.

The primary analysis will occur when all randomized subjects have had sufficient follow-up time to complete the Day 29 visit. Data collected during the extended FU period will be summarized separately, after the primary study analysis.

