8.3.1. Primary Efficacy Analysis

The primary efficacy objective of this study is to evaluate the efficacy of BEM based on the proportion of patients who are hospitalized for any cause or who died due to any cause through Day 29 in the supportive-care-only population. The primary estimand is the difference in the proportion of patients who are hospitalized for any cause or who died due to any cause through Day 29 in the supportive-care-only population, and the primary treatment effect comparison will be between the BEM arm and the placebo arm. This proportion will be compared between the BEM and placebo arms using a Cochran-Mantel-Haenszel (CMH) test adjusted for the stratification factors of age and region. The CMH p-value and estimated common risk difference, odds ratio and relative risk, along with the corresponding 95% confidence intervals (CIs) for these estimates, will be presented.

Intercurrent events are those that occur after treatment initiation and either preclude observation of the variable or affect its interpretation. For the intercurrent events of rescue (eg intervention with remdesivir) and concomitant COVID-19 medications, a treatment policy approach will be taken, whereby use of rescue and concomitant medications will be ignored and observations collected after they are administered to the patient will be used. In addition, patients will be followed, assessed, and analyzed irrespective of their completion of the course of the study treatment. The analysis will be performed based on observed data, and the following measures will be used to reduce missing hospitalization/death data: eCRFs capturing clinical information that may be indicative of hospitalization will be reviewed to mitigate the risk of unreported hospitalizations, and study staff may use a public information source to obtain information about survival status if a patient withdraws from the study.

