8.3.2. Secondary Efficacy Analyses

Analysis of the primary efficacy endpoint will be conducted for the combination antiviral population as a secondary endpoint. Presentation and analysis of other secondary efficacy endpoints will be carried out using methods similar to those specified for the primary efficacy endpoint. Data handling, analysis populations, and specification of statistical testing for secondary efficacy endpoints, with methods used to control overall type I error, will be detailed in the SAP.

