3.2.2. Secondary Endpoints

The secondary endpoints are:

Efficacy:

- Proportion of subjects with all-cause hospitalization or all-cause death through Day 60
- Proportion of subjects with all-cause hospitalization, all-cause death, or COVID-19 related medically attended visits through Day 29 and Day 60
- Proportion of subjects with COVID-19-related hospitalization or who died due to any cause death through Day 29 and Day 60
- Proportion of subjects who died due to any cause through Day 29 and Day 60
- Proportion of subjects with COVID-19-related complications (eg., death, hospitalization, radiologically confirmed pneumonia, acute respiratory failure, sepsis, coagulopathy, pericarditis/myocarditis, cardiac failure) through Day 29 and Day 60
- Proportion of subjects with COVID-19-related medically attended visits (hospitalization, emergency room (ER) visit, urgent care or physician's office visit or telemedicine visit) or who died due to any cause through Day 29 and Day 60
- Proportion of subjects with COVID-19 symptom relapse through Day 29
- Proportion of subjects with viral load rebound through Day 29.

Safety:

• The incidence and severity of adverse events (AEs) and serious adverse events (SAEs).

The primary endpoint will also be assessed in the combination antiviral population as a secondary endpoint. All secondary endpoints will be assessed in both the supportive-care-only population and the combination antiviral population.

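### Do the 12 combination-antiviral secondary tests left out of the SAP 8.5 sequence undermine the type I error control?

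*SAP*

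**What the plan says.** SAP 8.5 sets up a gate and a fixed order: "If a statistically significant result is found on the test of the primary endpoint, sequential testing will be performed for the secondary endpoints". The list has 11 items. Items 1 to 9 are each restricted to the supportive-care-only population. Items 10 and 11 are the only combination-stratum entries: "Proportion of subjects in the combination-antiviral population with COVID-19 symptom relapse through Day 29", and the matching item for viral load rebound. SAP 8.7 repeats the same items and gives them the primary-analysis method.

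SAP 3.2.2 is wider. It says "The primary endpoint will also be assessed in the combination antiviral population as a secondary endpoint", and then "All secondary endpoints will be assessed in both the supportive-care-only population and the combination antiviral population". SAP Table 2 has one combination row, for all-cause hospitalization or death, labelled secondary. It has no combination row for relapse or rebound.

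Protocol 8.3 adds "Efficacy analyses will be repeated using the mITT-C population". Protocol 8.3.2 leaves the testing rules to the SAP: "specification of statistical testing for secondary efficacy endpoints, with methods used to control overall type I error, will be detailed in the SAP". SAP 6.1 makes one-sided 0.025 the default level for any test.

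On the role of the stratum, protocol 1.5 treats the combination data as proof-of-concept and hypothesis-generating. SAP 8.3 states null and alternative hypotheses for the supportive-care population only.

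**The concern.** Protocol 8.3.2 names hospitalization or death in the combination population as a secondary endpoint, and in the same paragraph refers to type I error control for secondary endpoints. A reader then expects to find that endpoint in SAP 8.5. It is absent, while two less important combination endpoints are listed. Table 2 shows the opposite selection.

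Read literally, the SAP defaults (analyses on each stratum, tests at one-sided 0.025) would produce 12 further p-values with no gate and no label. The risk is that a value below 0.025 for combination hospitalization or death might be described as a secondary endpoint met, even after a failed primary.

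**Working it through.** **1. Check of the test convention.** The documents give no figure for the multiplicity point, so I checked the convention on the sample size in SAP 11.2. With rates 0.016 and 0.04 (mean 0.028), one-sided 0.025 and 90% power:

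n per arm = [1.960·√(2·0.028·0.972) + 1.2816·√(0.016·0.984 + 0.04·0.96)]² / 0.024² = 0.5707 / 0.000576 ≈ 991.

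This matches the SAP.

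**2. Count.** Combination-stratum efficacy tests implied by SAP 3.2.2:

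| Endpoint | Days | Tests |
|---|---|---|
| All-cause hospitalization or death | 29, 60 | 2 |
| The same or a COVID-19 visit | 29, 60 | 2 |
| COVID-19 hospitalization or any death | 29, 60 | 2 |
| Death | 29, 60 | 2 |
| COVID-19 complications | 29, 60 | 2 |
| COVID-19 visit or any death | 29, 60 | 2 |
| Symptom relapse | 29 | 1 |
| Viral load rebound | 29 | 1 |
| Total | | 14 |

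Two are placed in SAP 8.5, so 12 are not. The number becomes 14 if item 7 of SAP 8.5 (COVID-19 visits alone, two days) is also run in this stratum. The sequence itself holds 1 + 6×2 + 4×1 = 17 tests.

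**3. What the sequence protects.** In a fixed sequence at 0.025, a false claim requires rejecting the first true null in the order. The error over the primary and the 17 listed tests is therefore at most 0.025. An unlisted p-value gates nothing and takes no alpha from the list, so this bound holds whatever else is computed.

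**4. Size of the error if an unlisted test were promoted to a claim.** Exact enumeration of two binomials, one-sided Mantel-Haenszel test at 0.025, unstratified. The arm sizes are 1,050 (2100/2) for the primary and 150 (300/2, the planned maximum) for the combination stratum. The event rates are assumptions and are taken as equal in the two strata.

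| Event rate | Size, 1,050 per arm | Size, 150 per arm | Joint error 1−(1−s₁)(1−s₂) |
|---|---|---|---|
| 1% | 0.0256 | 0.0146 | 0.0399 |
| 2% | 0.0249 | 0.0228 | 0.0471 |
| 3% | 0.0249 | 0.0221 | 0.0464 |
| 4% | 0.0246 | 0.0236 | 0.0476 |

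The nominal value is 1 − 0.975² = 0.0494.

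Combination subjects all receive an antiviral, so lower rates are plausible. Protocol 1.1 quotes reductions of 57% to 86% for one such drug. Assuming these apply to the 4% planning rate, the combination rate is 4%×0.43 = 1.72% down to 4%×0.14 = 0.56%. The combination test's size is then 0.0226 and 0.0045. With 0.0246 for the primary, the joint error is 4.7% and 2.9%.

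**5. All 12 tests together.** If they were independent, the chance of at least one false positive would be 1 − 0.975¹² = 26%, but the endpoints are nested and overlap heavily. With a common correlation of 0.5, 0.7 or 0.9 between test statistics it is about 16%, 12% or 7%. A simulation of overlapping events under eight assumed sets of rates gave 6–14%. The documents supply neither rates nor overlap, so these figures only indicate scale.

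**6. Power.** At 4% versus 1.6%, power for combination hospitalization or death is 22% at 150 per arm and 21% at 143 per arm (95% of 300 evaluable). Expected events are 150×0.04 = 6 versus 150×0.016 = 2.4.

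**The case for a change.** The strongest case for a change is that nothing in writing confines SAP 8.5 to being the complete list of formal tests. Items 10 and 11 show that the authors did admit combination endpoints to the controlled family, so the list cannot be explained as supportive-care only. Protocol 8.3.2 says of the secondary endpoints "Presentation and analysis of other secondary efficacy endpoints will be carried out using methods similar to those specified for the primary efficacy endpoint", and the primary method yields "The CMH p-value and estimated common risk difference, odds ratio and relative risk", so p-values in the combination population are planned. The hypothesis-generating description sits in the protocol's rationale and is not repeated in SAP 6.1, 8.5 or 8.7. One sentence written before unblinding would remove the doubt.

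The factual part stands: the count is right, the status is unstated, and Table 2 and SAP 8.5 choose different combination endpoints. The inference does not follow. Protocol 8.3.2 leaves it to the SAP to specify the testing, and does not promise alpha control for every endpoint in both strata. SAP 8.5 makes that choice by naming endpoint and population item by item. SAP 3.2.2 says the endpoints are assessed in both populations, which calls for an estimate and perhaps a p-value, not a significance claim. SAP 6.1 fixes the level of a test and does not say which results support a claim. The Table 2 mismatch concerns how estimands are documented; its title limits it to the primary and key secondary endpoints.

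Adding combination hospitalization or death as a final step would be a preference with little return. It would be reached only after the primary and all 17 listed tests succeed, and would then have about 21–22% power.

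**Conclusion.** No change follows. The SAP leaves unstated the status of 12 combination-stratum tests, and analysts would fill that gap sensibly: an endpoint absent from a fixed sequence is reported with its estimate, confidence interval and a nominal p-value. This agrees with the role protocol 1.5 gives the stratum and with hypotheses stated only for supportive care.

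The primary and the 17 listed tests keep one-sided 0.025. No estimate, sample size or primary conclusion depends on the point. The joint error of 4.0–4.8% (150 per arm, assumed rates of 1–4%), or as little as 2.9% at an assumed combination rate of 0.56%, arises only if someone makes a formal claim that the plan does not make. A sentence stating the nominal status would be a harmless clarification, but it would alter no result.
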